10.4. SENSITIVITY ANALYSES

The primary analysis will be assessed in sensitivity analyses using different assumptions and populations:

- the primary analysis will be repeated on the mITT population. For this analysis, missing data for the primary endpoint will be imputed using the same procedure used for the interim analysis (see Section 15). This analysis will be performed to assess the robustness of the results to protocol deviations: mITT analysis provides a “real life” scenario, in which participants may not comply to the protocol.
- the proportion of subjects that are event-free at one year will be estimated by means of a logistic regression model including as covariates the implanted valve groups (Perceval or standard sutured stented valves) and the stratification factors:

- country, and
- surgical approach.

This method allows to assess the sensitivity of non-inferiority results to possible confounding impact of the stratification factors.

A 97.5% one-sided upper confidence limit will be computed from the logistic model for the difference ($MACCE_{CONTROL} - MACCE_{PERCEVAL}$). The non-inferiority of Perceval to the Control will be confirmed if the upper confidence limit is lower than 0.05 (Δ). This sensitivity analysis of non-inferiority will be assessed in the Per Protocol Population.

- the one-year freedom from MACCE will be evaluated using the Kaplan-Meier estimates for cumulative freedom from MACCE and the Greenwood standard errors for each arm (as planned in the CIP before amendment). A 97.5% one-sided upper confidence limit will be computed for the difference ($MACCE_{CONTROL} - MACCE_{PERCEVAL}$) where $MACCE_j$ is the survival estimated by the Kaplan-Meier algorithm for arm j. The Perceval arm will be confirmed not inferior to the Control if the upper confidence limit is lower than 0.05 (Δ).

The test statistic is

$$\frac{MACCE_{PERCEVAL} - MACCE_{CONTROL} + \Delta}{\sqrt{VAR(MACCE_{PERCEVAL}) + VAR(MACCE_{CONTROL})}}$$

where VAR()s are the variances estimated by Greenwood's formula. The null hypothesis will be rejected if the test statistic is greater than 1.96. This sensitivity analysis of non-inferiority will be assessed both in PP and mITT populations in order to confirm the robustness of results to statistical method and protocol deviations.

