10.3 EXPECTED DROP-OUT RATES

The considered attrition rate from enrollment to Per Protocol population will be 10% of subjects, which may include, but is not limited to subjects with failure to implant, lost to follow-up and discontinued subjects.

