15. INTERIM ANALYSIS

Two interim analyses will be performed to select the sample size. These interims will be triggered when the number of subjects enrolled will be approximately 900 and 1050 (interim analyses cut-off dates). The study will stop accrual for expected success if the posterior probability of non-inferiority in the PP population is sufficiently high. The threshold varies by interim: accrual will stop if the posterior probability exceeds

- 0.996 at N=900, or
- 0.993 at N=1050.

The analysis will be conducted by the external Independent Statistical Unit who will communicate to the Sponsor the result of the interim analysis and the consequent decision on the continuation of enrollment (i.e. “Stop enrolment for predicted success”, “Continue enrolment”).

As the interim analyses will only determine whether accrual needs to be stopped, then the interim analyses decisions have no impact on the subsequent study conduct. Therefore subject follow up will continue up to 5 years and the primary analysis will take place at the 12-month primary analysis.

At the time of each interim analysis, there will be subjects eligible for Per Protocol analysis population whose one-year outcome is unknown (e.g. ongoing subjects not having yet reached the one-year visit). For this reason at the interim analysis an imputation model will be used for their one-year outcome according to these rules:

- Any subjects that are missing the one-year outcome, but are known to have a MACCE event at an intermediate time point, will have their one-year outcome imputed as “not MACCE-free”.
- Any subjects that are missing the one-year outcome but have not had a MACCE event at an intermediate time point (3, 6, and 9 month intervals) will have their one-year outcome imputed, using multiple imputation. The probability that a subject remains MACCE-free at one year, conditional on being MACCE-free as of their last known intermediate time point (3, 6, and 9-month intervals), follows a Beta-Binomial distribution. A non-informative Beta(1,1) priors, separately within each arm is going to be applied. Additional details are provided in the CIP Appendix 8.

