18. ANALYSIS SPECIFICATIONS

The purpose of this section is to give technical details for the implementation of the SAP.

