18.5. HANDLING OF MISSING VALUES

At each time point/visit, all subjects still in the study are reported. Missing values will be taken into account as missing in the analysis. The number of observed values and the number of missing values must sum up to the number of subjects in the study at the respective time point/visit.

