Clinical efficacy (after 30 days)	
Serious Adverse Event (SAE):
 
YES if at least one (Time to SAE >30 days) per CEC or Echo core lab:
 
 - All-cause mortality - All stroke (disabling and nondisabling) - Requiring hospitalizations for valve-related symptoms or worsening congestive heart failure. - NYHA class III or IV (date of assessment >30 days after valve implant) - Valve-related dysfunction: 
 i. (mean aortic valve gradient ≥ 20 mm Hg, EOA ≤ 0.9–1.1 cm² and/or DVI < 0.35 m/s, AND/OR ii. moderate or severe prosthetic valve regurgitation) 
NO, otherwise

Derived variable	Derivation algorithm
Time-related valve safety	
Serious Adverse Event (SAE):
 
YES if at least one (Time to SAE >30 days) per CEC or echo core lab:
 
 - Structural valve deterioration (both points i. and ii. have to be met): 
 i. Valve-related dysfunction: 
 ▪ mean aortic valve gradient ≥ 20 mm Hg, EOA ≤ 0.9(if BSA<1.6 cm²) or 1.1(if BSA≥ 1.6 cm²) cm² and/or DVI<0.35 m/s, AND/OR ▪ moderate or severe prosthetic valve regurgitation) ii. Requiring repeat procedure (TAVI or SAVR) - Prosthetic valve endocarditis - Prosthetic valve thrombosis - Thrombo-embolic event, non-cerebral , - TIA - STROKE - VARC bleeding (BARC type 5, BARC type 3A, 3B and 3C, BARC type 2), unless clearly unrelated to valve therapy (e.g., trauma) : Device and/or procedure related 
NO, otherwise

MACCE (Yes/No)	
Serious Adverse Event (SAE), Valve re-intervention:
 
YES if at least one per CEC:
 
 - Death - Myocardial infarction - Stroke - Reintervention 
NO, otherwise

Derived variable	Derivation algorithm
MACCE @ 1 year (Yes/No)	
Serious Adverse Event (SAE), Valve re-intervention:
 
YES if at least one per CEC:
 
 - Death (Time to SAE <=365 days) - Myocardial infarction (Time to SAE <=365 days) per CEC - Stroke (Time to SAE <=365 days) per CEC - Reintervention (Time to SAE <=365 days) 
NO, otherwise

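### The SAP's one-year MACCE derivation has no missing level, which contradicts the imputation planned for the mITT repeat of the primary analysis

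*SAP*

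**What the plan says.** **The imputation rule.** SAP 10.4 repeats the primary Bayesian analysis on the mITT population, where "missing data for the primary endpoint will be imputed using the same procedure used for the interim analysis (see Section 15". Section 15 then covers "Any subjects that are missing the one-year outcome but have not had a MACCE event at an intermediate time point": they are multiply imputed by arm from a Beta-Binomial model, conditional on being event-free at the last known 3-, 6- or 9-month interval.

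**The derivation.** Table 8 in SAP 18.12 has a row headed "MACCE @ 1 year (Yes/No". It is YES if an adjudicated death, myocardial infarction, stroke or re-intervention falls inside the window (for example "Reintervention (Time to SAE <=365 days") and NO in every other case. There is no third level and no condition on last contact. Section 18 opens with "The purpose of this section is to give technical details for the implementation of the SAP", so the table is the programmer's specification.

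**Related text.**
- SAP 18.5 says "Missing values will be taken into account as missing in the analysis", but in a paragraph about subjects still in the study at a given visit.
- The mITT population (SAP 6.4) requires a study valve and no minimum follow-up. The PP population (SAP 6.5) requires attendance up to one year.
- The Kaplan-Meier sensitivity analysis is run on both PP and mITT (SAP 10.4). SAP 5.2 censors subjects who discontinue without an event.
- Protocol 10.3 allows 10% attrition from enrollment to PP, "which may include, but is not limited to subjects with failure to implant, lost to follow-up and discontinued subjects".

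**The concern.** A variable that is only ever YES or NO gives an imputation procedure no input. Take an mITT patient who withdraws event-free at day 40. Under Table 8 the patient is NO, hence MACCE-free at one year. Under 10.4 and 15 the patient has a missing outcome and is imputed.

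No visible passage says when a one-year outcome counts as missing at the final analysis. The only example in Section 15, "e.g. ongoing subjects not having yet reached the one-year visit", describes a group that should no longer exist when the primary analysis is run, since SAP 4.1 places that analysis after all subjects complete 12 months. Those who remain are withdrawn and lost patients, and the plan never assigns them a missing value.

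Protocol 10.4.2 makes mITT the key sensitivity population, and Protocol 10.8 expects no missing data in PP. The mITT repeat is therefore where losses to follow-up are meant to be tested. Scoring them as successes lowers the observed event rate in both arms. With equal loss this shrinks a true Perceval deficit and makes the check easier to pass.

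**Working it through.** **1. Reproduce the plan's own figure.** SAP Table 1 gives Pr(success) 0.805 at 0.91/0.91. With 1234 × 0.9 / 2 ≈ 555 per arm, the SAP 10.3 prior, the 0.9775 threshold, no interim looks and exact binomial enumeration, I get 0.817. At 0.91/0.86 I get 0.0235, against 0.023 stated. The decision rule is reproduced closely enough to use. No design figure is in dispute.

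**2. Inputs for the mITT repeat.** From the documents: margin 0.05, threshold 0.9775, maximum enrolment 1234 allocated 1:1 (617 per arm), and true event-free rates 0.91 and 0.86. Assumed, because the documents give neither: the loss rate in each arm (L), and the share of events that would fall after the loss and so go unseen (s). Loss is taken as unrelated to outcome.

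**3. Formulas, if the Table 8 flag is the analysis variable.**
- Observed event rate in an arm: e = true event rate × (1 − L × s)
- Observed deficit: d = e(Perceval) − e(control)
- SE = √[e_C(1 − e_C)/617 + e_P(1 − e_P)/617]
- False support = P(Z > 2.005 − (0.05 − d)/SE), where 2.005 is the normal quantile for 0.9775

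Example, 10% loss in each arm, s = 1: e_C = 0.09 × 0.9 = 0.081; e_P = 0.14 × 0.9 = 0.126; d = 0.045; SE = 0.0173; 0.005/0.0173 = 0.289; P(Z > 1.716) = 4.3%.

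| Loss control / Perceval | s | e_C | e_P | d (points) | False support |
|---|---|---|---|---|---|
| none | – | 9.00% | 14.00% | 5.00 | 2.25% |
| 5% / 5% | 1 | 8.55% | 13.30% | 4.75 | 3.1% |
| 10% / 10% | 1 | 8.10% | 12.60% | 4.50 | 4.3% |
| 2% / 8% | 1 | 8.82% | 12.88% | 4.06 | 7.0% |
| 8% / 2% | 1 | 8.28% | 13.72% | 5.44 | 1.2% |
| 5% / 5% | 0.5 | 8.775% | 13.65% | 4.875 | 2.65% |
| 10% / 10% | 0.5 | 8.55% | 13.30% | 4.75 | 3.1% |
| 2% / 8% | 0.5 | 8.91% | 13.44% | 4.53 | 4.1% |
| 8% / 2% | 0.5 | 8.64% | 13.86% | 5.22 | 1.7% |

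**4. Exact check.** Enumerating the Bayesian rule at 617 per arm gives 2.34% with no loss. At s = 1 it gives 3.2% for 5%/5% and 4.5% for 10%/10%. If 40% of events fall in month 1 and loss is uniform over months 1–12, these become 2.6% and 2.85%. For 5% control / 10% Perceval the range over the timing assumptions is 3.4% to 7.4%.

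**5. Same data, two rules.** Simulation (4000 runs, standard error about 0.3 points; 40% early events, uniform loss) compared the NO default with imputation by the Section 15 rule. At 10%/10% loss, false support is 2.8% against 2.2%. At 5% control / 15% Perceval it is 4.3% against 1.9%. In these two cases the excess comes from the default, and imputing as 10.4 asks removes it.

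**The case against.** A reader might infer from Table 8 that the plan counts lost patients as successes. The documents do not support that. SAP 10.4 and 15 prescribe imputation for this analysis, and a programmer who follows them would impute. A strictly literal Table 8 would also leave nothing to impute at the interims, where Section 15 expects unknown outcomes, so the literal reading is probably not the intended one. The row could be meant only to classify recorded events. Another Table 8 row builds the MACCE-free denominator by adding patients with an event to those without one at day 365, which hints that status must be known, though it does not say so. Protocol Appendix 8, whose content is not in the available text, may say more. This stands: the finding is an unreconciled contradiction, and its consequence depends on which rule is programmed.

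The size is also open to challenge. The 10% in Protocol 10.3 includes failed implants and is not a loss-to-follow-up rate. Having every loss precede every event (s = 1) is extreme after surgery: Protocol 6.2 reports 3.4% early mortality and 1.2% early stroke in pooled Perceval data. The direction is not fixed either, since heavier control loss makes the check conservative. All of this stands and is why ranges are given.

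Nor may a reader take 7% as the trial's type I error. Non-inferiority is decided on PP, and 10.4 sets no separate pass rule for the mITT repeat. The Kaplan-Meier mITT analysis handles the same patients by censoring.

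**Conclusion.** The contradiction is real. Table 8 cannot yield a missing one-year outcome, SAP 10.4 and 15 need one, and nothing visible says which prevails or who is missing at the final analysis. If the flag is used as the analysis variable, false support from the mITT repeat rises from about 2.3% to roughly 2.7–4.5% for 5–10% equal loss (2.6% at the mildest timing examined). It reaches about 7% for 8% Perceval against 2% control loss and falls to about 1.2% with those reversed. These figures rest on assumed loss rates and event timing, rates at the margin, and 617 per arm.

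The reach is limited to one sensitivity analysis, with an unaffected Kaplan-Meier counterpart. One gap could widen it: the Table 8 PP flag omits the one-year attendance condition in SAP 6.5. The NO default could then enter the primary analysis unless a missed visit is recorded as a major deviation. SAP 6.5 lists incomplete endpoint assessments among those deviations, so this is a loose end rather than a demonstrated error. The contradiction should be resolved before database lock.

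**What to change.** In the Table 8 row for one-year MACCE, define three levels:
- **YES:** an adjudicated component by day 365.
- **NO:** no event, and either a completed 1-year visit within the SAP window or documented contact at or after day 365.
- **MISSING:** otherwise.

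The SAP window is day 365 ± 30, so a visit at day 335 leaves up to 30 days in which events would count but were not observed. A bare day-335 follow-up cut-off is therefore not enough for NO: before day 365, only a completed 1-year visit should qualify. Report how many NO subjects have no contact after day 364.

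Then state that MISSING subjects are the ones imputed under SAP 10.4 and 15, report the number imputed by arm, and add the SAP 6.5 one-year attendance condition to the Table 8 PP flag.

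The cost is two edited derivation rows, one sentence in 10.4 and a count in the output. The imputation is already planned, and the changes listed here add no visits to the schedule.

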11. SECONDARY EFFICACY ANALYSES

The following secondary efficacy analyses will be performed:

- each component of the primary endpoint will be analyzed as binomial proportion (95% C.I.) of subjects event-free at one year (section 18.12);
- primary endpoint will be analyzed annually as binomial proportion (95% C.I.) of subjects event-free at 1, 2, 3, 4 and 5 years of follow-up (section 18.12);
- The time to the first MACCE will be analyzed using all data collected up to analysis cutoff date (patients may have more that 1-year follow-up):
 - by means of time-to-event methods (see section 5.2)
 - with a Cox regression model, using the stratification factors (country and surgical approach) and pre-operative variables (including demographic, medical history, and concomitant procedures) as covariates. Countries with less than 20 enrolled patients will be pooled. The assumptions of proportionality will also be investigated with a time-dependent exploratory variable, which is defined as $\text{treatment} * \{\log[\text{time to event}]\}$. If the p-value from the Wald Chi-squared statistic for this variable is less than 5% there is

evidence of a departure from the adjusted model assumptions. In case of non-proportional hazards, a Weibull model will be assumed as parametric form of the distribution of survival times. The treatment group will be included in the model as covariate.

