10.1.6 SUMMARY STATISTICS

Descriptive statistics will be calculated using as reference the number of subjects in the relevant analysis population (any exception will be specified) according to the nature of each parameter as follows:

- For quantitative (continuous) parameters: Number of subjects with available and missing data, mean, standard deviation (SD), median, quartiles (Q1-Q3) and extreme values [Minimum; Maximum];
- For qualitative (discrete) parameters: Number of subjects and frequency (percentage);
- For Time-to-event variables: Cumulative freedom from events will be evaluated using the method of Kaplan-Meier. The degree of uncertainty in each actuarial analysis will be expressed with 95% confidence limits. The 95% confidence interval bounds for the cumulative freedom will be calculated per the method proposed by Greenwood [25]. Comparison of curves among arms will be performed with the log-rank test. Kaplan-Meier graphs will be presented along with the number of patients-at-risk at exact time points. Covariate analyses will be based on the proportional hazards model. Arms will be compared using multivariate Cox proportional hazards regression. The hazard ratio (95% C.I.) will be presented.
- For Bayesian analyses: posterior means, standard deviations, and 95% credible intervals will be reported.

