5.2. DESCRIPTIVE STATISTICS

Descriptive statistics will be calculated using as reference the number of subjects in the relevant analysis population (any exception will be specified) according to the nature of the data as follows:

- Continuous variables: number of non-missing observations, arithmetic mean, standard deviation, minimum and maximum values, median and quartiles. If there are less than 5 observations, only the number of non-missing observations, arithmetic mean, median, minimum and maximum will be presented.
- Categorical variables: Number of missing and non-missing observations the relevant percentage on the analysis population. In case of subcategories, the relative frequencies will be calculated on the basis of the subjects in the subcategory, in this case a footnote will be added explaining the different denominators.
- Time-to-event variables: number of non-missing observations, minimum, first quartile, median including 95% confidence interval, third quartile, and maximum. For calculating the survival estimate CI bounds the log-log transformed estimate of CI bounds will be used. In addition, Kaplan-Meier estimates and plots will be provided with:
 - the 95% confidence interval bounds calculated per the method proposed by Greenwood⁸
 - the respective number of patients at risk and Kaplan-Meier estimates at different time points (at least every 5 months or more frequently)
 - the median and its 95% confidence interval.
 - the log-rank test p-value
 - the Hazard Ratio (HR), its 95% confidence interval and the relevant p-value.

Subjects ongoing and who are free from event at the analysis cut-off date will be censored at the analysis cut-off date. Subjects who have discontinued without an event will be censored at the date of discontinuation.

- For Bayesian analyses: posterior means, standard deviations, and 95% credible intervals will be reported.

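### If proportional hazards is rejected, the SAP's fallback Weibull model, on its ordinary reading, still imposes one constant hazard ratio and so does not address the violation

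*SAP*

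**What the plan says.** SAP section 11 specifies the following for time to first MACCE:

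- **Data.** "The time to the first MACCE will be analyzed using all data collected up to analysis cutoff date", so some subjects contribute more than one year.
- **Model.** The analysis is done "with a Cox regression model, using the stratification factors (country and surgical approach) and pre-operative variables".
- **Check.** "The assumptions of proportionality will also be investigated with a time-dependent exploratory variable", defined as treatment multiplied by the log of time.
- **Trigger.** "If the p-value from the Wald Chi-squared statistic for this variable is less than 5% there is" taken to be a departure from the model's assumptions.
- **Fallback.** "In case of non-proportional hazards, a Weibull model will be assumed as parametric form of the distribution of survival times". The next sentence reads: "The treatment group will be included in the model as covariate".

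For this case the SAP gives no arm-specific shape or scale, stratification by arm, treatment-by-time term, phase-specific HR or restricted mean survival time (RMST). SAP section 5.2 lists the effect measure for time-to-event variables as "the Hazard Ratio (HR), its 95% confidence interval and the relevant p-value". Protocol section 10.1.6 says "Arms will be compared using multivariate Cox proportional hazards regression" and describes no fallback.

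**The concern.** The test asks whether the HR between arms changes with time. The remedy should then be a model or summary in which it may change. A Weibull regression with treatment in the linear predictor does not allow that. It swaps the unspecified Cox baseline hazard for a parametric one, so it adds an assumption and keeps the one that has just been rejected.

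The trigger is foreseeable here. Protocol section 9.1 expects shorter cross-clamping to reduce in-hospital MACCE, which is an early effect, while the composite also counts deaths, strokes, infarctions and re-interventions long after surgery. SAP section 18.12 already separates events at 30 days. If the effect does differ by phase, the adjusted HR reported under the fallback would be an average whose value depends on how long subjects happened to be followed.

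**Working it through.** The documents give no figure on this point, so there is none to reproduce. The claim is algebraic; the numbers only illustrate it.

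**1. The fallback has a constant HR.** With a common shape k and treatment indicator x, the hazard is h(t|x) = λ·k·t^(k−1)·exp(b·x). Hence h(t|1)/h(t|0) = exp(b) at every t. With b = −0.3 the ratio is 0.7408 at 0.02, 0.08, 0.25, 1 and 2 years, for each of the shapes 0.5, 1 and 1.5. The accelerated-failure-time form with constant scale s and coefficient g gives HR = exp(−g/s), again free of t.

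**2. Example with a change at day 30.** All inputs are assumed: control risk 5% up to day 30 and 5% from day 31 to 365 among those still event-free; true HR 0.5 in the first phase and 1.6 afterwards, continuing beyond one year.

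- One-year event-free, control: 0.95 × 0.95 = 0.9025, or 90.3%.
- One-year event-free, treated: 0.95^0.5 × 0.95^1.6 = 0.95^2.1 = 0.898, or 89.8%.
- One-year RMST (area under each curve to day 365): 339.5 days control, 343.1 days treated.

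Large-sample HRs from the two models, with everyone followed to the stated time:

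| Follow-up | Common-shape Weibull | Cox |
|---|---|---|
| 1 year | 1.03–1.04 | 1.04 |
| 27 months | 1.25 (shape 0.64) | 1.25 |
| 5 years | 1.39 | 1.40 |

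The fallback reproduces the Cox HR almost exactly. Neither model returns 0.5 or 1.6, and the value moves with follow-up alone.

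**3. A second mechanism.** Assume Weibull times with shape 0.35 in control and 0.80 in the Perceval arm, 9% events by one year in both, and censoring uniform over one to three years. The true HR then rises from 0.74 at 30 days to 3.12 at two years. The common-shape Weibull gives 1.33 for all times. In a sample of 5,000 per arm, Cox gave 1.335 and the Weibull 1.334.

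**4. A Weibull that would work.** If the shape differs by arm (k0, k1), then HR(t) = exp(b)·(k1/k0)·t^(k1−k0), so log HR is linear in log t. That is the departure which the treatment-by-log(time) term tests. Fitted to the data in step 3:

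| Time | 30 days | 3 months | 6 months | 1 year | 2 years |
|---|---|---|---|---|---|
| True HR | 0.74 | 1.23 | 1.67 | 2.29 | 3.12 |
| Arm-specific shape | 0.74 | 1.23 | 1.68 | 2.31 | 3.16 |

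**The case against.** Four arguments deserve weight.

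**The SAP never states a common shape.** It could be read as merely under-specified. The Cox sentence does not list treatment among its covariates, so the sentence adding treatment might be meant for either model. This stands in part: an arm-specific shape would be coherent. But a covariate ordinarily acts on the linear predictor, and nothing in the text lets the shape depend on arm. The rule needs correcting on either reading.

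**A reader might infer that the plan could hide opposite early and late effects.** The documents do not support that. Regardless of the test, the SAP plans Kaplan-Meier curves with numbers at risk (5.2), MACCE-free proportions at one to five years (11), adverse events by early and late phase (13.1.2), and 30-day safety and post-30-day efficacy composites (18.12). A reversal would show there, and the fitted interaction term would itself give the direction of change.

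**A reader might infer that the non-inferiority conclusion is at risk.** It is not. The primary analysis compares one-year proportions (SAP 10.3). The sensitivity analyses repeat that comparison or use logistic regression and a Kaplan-Meier difference at one year (SAP 10.4). The Cox model carries no success criterion.

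**The example can be made to look more dramatic than it is.** Setting the 27-month HR of 1.25 beside nearly equal one-year event-free rates mixes horizons. At one year the HR is about 1.04, in line with 90.3% against 89.8%. The 0.5/1.6 reversal is also assumed; no figure in the documents supports an effect of that size. The constant-HR result does not depend on it.

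**Conclusion.** The point holds for one conditional secondary analysis. Under the ordinary common-shape reading, the fallback in SAP section 11 is another proportional-hazards model. If the 5% test rejects, the plan would report an adjusted HR close to the Cox HR it replaces, and the violation would remain.

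The size for this trial cannot be stated, because it depends on an unknown time pattern. In the assumed example the single HR runs from about 1.04 to 1.39 as follow-up lengthens from one to five years, with true phase values of 0.5 and 1.6.

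The damage is confined to that adjusted HR. It is worth correcting because the rule as written does not do what it is there to do, and because choosing a replacement after seeing a failed test would be a post hoc choice.

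**What to change.** Replace the Weibull sentence in SAP section 11 with a rule that lets the treatment effect vary with time and keeps the planned covariates. Suggested wording:

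*If proportionality is rejected, treatment HRs for time to first MACCE will be reported separately for up to 30 days and after 30 days, from a model adjusted for the same stratification factors and pre-operative variables.*

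This uses the SAP's existing early/late split. Two alternatives serve equally well: report the HR from the fitted treatment-by-log(time) model at stated times, or keep the Weibull model but let its shape differ by arm. A one-year RMST difference may be added as an optional summary; it is not needed to cure the fault. The SAP should also state that treatment is in the Cox model.

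The change costs one sentence and standard SAS or R procedures, with no new data. The real price is precision. At the maximum size, 1234 × 0.9 ≈ 1111 per-protocol subjects with 9% events give about 100 first events in year one. If, as an assumption, half fell in each phase, the standard error of a phase-specific log HR would be about 2/√50 = 0.28, against 2/√100 = 0.20 for the single HR.
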